## 7. RATIONALE AND BACKGROUND

Chronic obstructive pulmonary disease (COPD) is a common disease characterized by airway obstruction confirmed by spirometry, often including small airway obstruction, chronic bronchitis and emphysema (**Barnes 2015**). No known medications can reverse COPD, but regular maintenance treatments can help manage symptoms, reduce frequency of COPD exacerbations and improve health-related quality of life. Inhaled therapies are the cornerstone of COPD disease management approaches. The aim of inhaled therapy is to deliver agents directly to the lungs, thereby offering benefits while minimizing the potential for treatment-related adverse effects (**Braido 2016**).

Adherence to obstructive lung disease therapies involves patients initiating their prescribed therapy, implementing it as prescribed (i.e. correctly administering the prescribed dose at the physician directed frequency), and persisting with treatment (**Braido 2016; Mäkelä 2013**). Central to the therapeutic benefit of inhaled therapies is their successful administration which requires patients to have knowledge and understanding of (and ability to implement) the appropriate inhaler technique required to optimize both the dispensed and administered doses (**Braido 2016**). Inspiratory capabilities of patients with COPD are affected by increasing static and dynamic hyperinflation and weakening of the respiratory muscles, causing many patients to have peak inspiratory flow rates that are suboptimal to use many dry-powder inhalers (DPIs) (**Sohini 2017**). This paradoxical situation may lead to improper inhalation that prevents successful drug delivery to the lungs, which may affect treatment effectiveness. On the other hand, soft mist inhalers (SMI) force a metered dose of drug solution through a precise nozzle to deliver consistent and reliable doses to the lungs with each actuation (**Dalby 2004**) and may help preserve benefits in patients with diminished peak inspiratory flow rates.

Stiolto® Respimat®, a combination of Olodaterol and Tiotropium Bromide delivered via soft mist inhaler (SMI), was approved in May 2015 in the US and July 2015 in the EU (marketed

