### Matched Cohort

A matched propensity score analysis will be used to assess comparative persistence between the two exposure comparison groups. Logistic regression will be used to calculate the propensity to initiate Olodaterol/Tiotropium Bromide versus Umeclidinium/Vilanterol given all covariates (except components of the Charlson Comorbidity index) listed in [section 9.3.3](#), according to the following model:

$$\text{Logit}(\text{Treatment} | X_1, X_2, \dots, X_n) = \beta_0 + \beta_1 * X_1 + \beta_2 * X_2 + \dots + \beta_n * X_n$$

Any covariates which are collinear with each other will be dropped from the analysis (if it causes failure of model to converge). The propensity score will then be used to identify up to 2 initiators of Umeclidinium/Vilanterol for each initiator of Olodaterol/Tiotropium Bromide with the same propensity score ( $\pm$  a caliper of 5%) as the corresponding initiator of Olodaterol/Tiotropium Bromide (Austin 2011).

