#### **9.3.3 Covariates**

Covariates will be identified based on data recorded within 180 days prior to or on the index date (date of dispensing/initiation of the exposure), unless otherwise specified. If multiple measurements are made in the baseline period, then the most recent measurement will be used.

Covariates will be used to predict propensity scores in later analyses. Absolute and relative frequencies of each covariate will also be reported in Table Shells 1 and 2 (see [Annex 5](#)). Detailed descriptions of the listed covariates can be found in [Annex 3](#) and [4](#).

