#### **Concomitant Medications**

- Oral Corticosteroids
- Short acting muscarinic antagonist (SAMA)
- Short acting beta agonist (SABA)
- Long acting muscarinic antagonist (LAMA)
- Long acting beta agonist (LABA)
- Inhaled corticosteroid (ICS)
- LAMA / LABA combination (that is not Stiolto or Anoro)
- LABA / ICS combination
- LAMA / LABA / ICS combination
- NSAIDs
- Antihistamines
- Opioids
- Oral antibiotics
- Antidiabetic Agents (not including insulin)

- Insulin (basal or mealtime)
- Methotrexate
- Statins
- Antihypertensives
- Anticoagulants
- Anti-psychotic/anti-depressives/anxiolytic
- Oxygen therapy

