#### 9.7.1.1 Descriptive Analysis

All variables specified in [section 9.3.3](#) will be reported. For demographic and lifestyle variables, the value recorded on the cohort entry date will be reported, otherwise the most recent known value will be reported. Presence of comorbidities and use of concomitant medication use will be determined based whether they ever occurred within the 180-day baseline period preceding the index date. Differences in the confounder distributions were inspected for successful confounder balance of measured characteristics.

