### ANNEX 3. LIST OF MEDICATION MEASURE DEFINITIONS

Name	Components
Corticosteroids	Betamethasone, *beclometasone (beclomethasone), cortisone acetate, dexamethasone, hydrocortisone, methylprednisolone, prednisolone, prednisone, triamcinolone, deflazacort, fludrocortisone
Short Acting Beta Agonist	Albuterol, metaproterenol, levalbuterol, pirbuterol, terbutaline
Short Acting Muscarinic Antagonist	Ipratropium
Long Acting Muscarinic Antagonist (LAMA)	Umeclidinium, glycopyrrolate, tiotropium, aclidinium, Incruse, Seebri, Spiriva, Tudorza
Long Acting Beta Agonist (LABA)	Indacaterol, arformoterol, formoterol, salmeterol, olodaterol, Arcapta, Atimos, Brovana, Perforomist, Serevent, Striverdi, Foradil
Inhaled Corticosteroids	Flunisolide, budesonide, mometasone, ciclesonide, fluticasone, beclomethasone, Aerobid, Aerospan, Alvesco, Armonair, Arnuity, Asmanex, Azmacort, Flixotide, Flovent, Pulmicort, Qvar
LAMA / LABA combination	indacaterol/glycopyrrolate, glycopyrrolate/formoterol, Utibron, Bevespi
LABA / ICS combination	Fluticasone/vilanterol, budesonide/formoterol, fluticasone/salmeterol, mometasone/formoterol, Advair, Symbicort, Breo, Dulera
LAMA / LABA / ICS combination	Fluticasone/umeclidinium/vilanterol, Trelegy
NSAIDs	Phenylbutazone, sulindac, tolmetin, diclofenac, etodolac, ketorolac, piroxicam, meloxicam, ibuprofen, naproxen, ketoprofen, fenoprofen, suprofen, flurbiprofen, oxaprozin, mefanamic acid, meclofenamic acid, celecoxib, rofecoxib, valdecoxib, nabumetone, glucosamine sulfate

Opioids	Morphine, hydromorphone, oxycodone, dihydrocodeine, fentanyl, pentazocine, buprenorphine, butorphanol, nalbuphine, tramadol, tapentadol, hydrocodone, codeine
Antihistamines/Antiallergic s	Diphenhydramine, clemastine, carboxamine, doxylamine, brompheniramine, dexchlorpheniramine, pheniramine, tripeptenamine, promethazine, thiethylperazine, cyclizine, chlorcyclizine, cetirizine, cyproheptadine, phenindamine, triprolidine, azatadine, astemizole, terfenadine, loratadine, ketotifen, azelastine, levocabastine, epinastine, fexofenadine, desloratadine, ephedrine, phenylephrine, oxymetazoline, xylometazoline, naphazoline, nedocromil

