Anticoagulants	Vitamin K antagonists (phenindione, warfarin), heparins (heparin, antithrombin III, dalteparin, enoxaparin, danaparoid, tinzaparin), platelet aggregation inhibitors (clopidogrel, ticlopidine, dipyridamole, epoprostenol, iloprost, abciximab, eptifibatide, tirofiban, treprostil, prasugrel, cilostazol, ticagrelor, cangrelor, vorapaxar, seleipipag), direct thrombin

	inhibitors (desirudin, lepirudin, argatroban, bivalirudin, dabigatran etexilate), direct factor Xa inhibitors (rivaroxaban, apixaban, edoxaban), anticoagulant enzymes (anistreplase, urokinase, reteplase, drotrecogin alfa, tenecteplase), defibrotide, fondaparinux
Statins	Atorvastatin, fluvastatin, lovastatin, pravastatin, rosuvastatin, simvastatin, pitavastatin, cerivastatin
Antihypertensives	Angiotensin converting enzyme (ACE) inhibitors, angiotensin receptor blockers, beta-blockers, calcium channel blockers, diuretics, alpha-blockers, alpha-beta blockers, vasodilators
Anti-psychotics/ Anti-depressives/Anxiolytics	Desipramine, clomipramine, trimipramine, amitriptyline, nortriptyline, protriptyline, doxepin, amoxapine, maprotiline, fluoxetine, citalopram, paroxetine, sertraline, fluvoxamine, escitalopram, isocarboxazid, phenelzine, tranylcypromine, tryptophan, trazodone, nefazodone, minaprine, mirtazapine, bupropion, venlafaxine, milnacipran, duloxetine, desvenlafaxine, vilazodone, vortioxetine, selegiline, chlorpromazine, promazine, acepromazine, triflupromazine, fluphenazine, perphenazine, prochlorperazine, trifluoperazine, thioridazine, mesoridazine, pipotiazine, haloperidol, droperidol, molindone, ziprasidone, lurasidone, thiothixene, pimozide, loxapine, clozapine, olanzapine, quetiapine, asenapine, lithium, risperidone, aripiprazole, paliperidone, iloperidone, cariprazine, brexpiprazole, pimavanserin, diazepam, chlordiazepoxide, oxazepam, lorazepam, clobazam, alprazolam, halazepam, hydroxyzine, meprobamate, buspirone
Oxygen Therapy	Oxygen

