End Stage Renal Disease	
1 Inpatient or 2 Outpatient (30 – 365 days apart)
 
Diagnosis Code (Any Position), ICD-9 is any of: { “403.01”, “403.91”, “458.21”, “585.5”, “585.6”, “996.56”, “996.68”, “996.73”, “V42.0”, “V45.1”, “V45.11”, “V45.12”, “V56”, “V56.0”, “V56.1”, “V56.2”, “V56.3”, “V56.31”, “V56.32”, “V56.8” }
 
Diagnosis Code (Any Position), ICD-10 is any of: { “I12.0”, “N18.5”, “N18.6”, “T86.10”, “T86.11”, “T86.12”, “Z49.01”, “Z49.02”, “Z49.31”, “Z49.32”, “Z91.15”, “Z94.0”, “Z99.2” }
 
Procedure Code (Any Position), ICD-9 is any of: { “55.69”, “55.6”, “38.95”, “39.27”, “39.42”, “39.43”, “39.95”, “54.98” }
 
Procedure Code (Any Position), ICD-10 is any of: { “05HY33Z”, “06HY33Z”, “0TS00ZZ”, “0TS10ZZ”, “0TY00Z0”, “0TY00Z1”, “0TY00Z2”, “0TY10Z0”, “0TY10Z1”, “0TY10Z2”, “3E1M39Z”, “5A1D00Z”, “5A1D60Z” }
 
Procedure Code (Any Position), CPT and HCPC is any of: { “36145”, “36800”, “36810”, “36815”, “36825”, “36830”, “36831”, “36832”, “36833”, “50323”, “50325”, “50327”, “50328”, “50329”, “50340”, “50360”, “50365”, “90918”, “90919”, “90920”, “90921”, “90922”, “90923”, “90924”, “90925”, “90935”, “90937”, “90939”, “90940”, “90945”, “90947”, “90951”, “90952”, “90953”, “90954”, “90955”, “90956”, “90957”, “90958”, “90959”, “90960”, “90961”, “90962”, “90963”, “90964”, “90965”, “90966”, “90967”, “90968”, “90969”, “90970”, “90989”, “90993”, “90997”, “90999”, “93990”, “99512”, “A4653”, “A4656”, “A4657”, “A4670”, “A4671”, “A4672”, “A4673”, “A4674”, “A4680”, “A4706”, “A4707”, “A4708”, “A4709”, “A4712”, “A4714”, “A4719”, “A4720”, “A4721”, “A4722”, “A4723”, “A4724”, “A4725”, “A4726”, “A4728”, “A4730”, “A4736”, “A4737”, “A4740”, “A4750”, “A4755”, “A4760”, “A4765”, “A4766”, “A4770”, “A4771”, “A4773”, “A4774”, “A4802”, “A4860”, “A4870”, “A4890”, “A4911”, “A4913”, “A4918”, “A4928”, “A4929”, “C1881”, “E1500”, “E1520”, “E1530”, “E1540”, “E1550”, “E1560”, “E1570”, “E1575”, “E1580”, “E1600”, “E1610”, “E1615”, “E1620”, “E1625”, “E1634”, }

	“E1635”, “E1636”, “E1637”, “E1639”, “E1699”, “G0257”, “G0308”, “G0309”, “G0310”, “G0311”, “G0312”, “G0313”, “G0314”, “G0315”, “G0316”, “G0317”, “G0318”, “G0319”, “G0320”, “G0321”, “G0323”, “G0324”, “G0325”, “G0326”, “G0327”, “G8727”, “G9013”, “G9014”, “J0635”, “J0636”, “S2065”, “S9335”, “S9339”, “E1638”, “G0322” }

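### Oxygen therapy, a propensity-score covariate, is defined only by the name 'Oxygen' in the medication list, so use recorded only under equipment, procedure or diagnosis codes would be coded 'no'

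*Combined protocol and SAP*

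**What the plan says.** Section 9.3.3 lists "Oxygen therapy" under Concomitant Medications and refers to the annexes for definitions: "Detailed descriptions of the listed covariates can be found in" Annexes 3 and 4. Annex 3 is titled "LIST OF MEDICATION MEASURE DEFINITIONS" and has two columns, a name and its components. The oxygen row reads "Oxygen Therapy Oxygen" and nothing more. Annex 4 has no oxygen measure.

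The propensity score is estimated "given all covariates (except components of the Charlson Comorbidity index) listed in" section 9.3.3. Oxygen is not a Charlson component, so it is in the score. By the same rule it is in the multivariable Cox and logistic models of section 9.7.1.3. Under section 9.7.1.1, "use of concomitant medication use will be determined based whether they ever occurred within the 180-day baseline period".

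Other measures are coded differently. The end-stage renal disease entry in Annex 4 has a long CPT and HCPCS list that includes dialysis equipment ("E1500”, “E1520”, “E1530”, “E1540" and onwards). Smoking, vaccination and pulmonary function tests also have procedure codes. Section 9.4 names Outpatient Services among the tables available for analysis.

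**The concern.** A name in a medication list finds records that carry that name. Oxygen use that reaches the database only as an equipment, procedure or diagnosis code would not be found. Because the covariate is present or absent by occurrence, those patients become 'no' rather than 'missing', so the missing-data rules of section 9.6 give no warning.

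Section 9.12 describes the covariates as hypothesized confounders. The matched Cox model contains treatment alone, so whatever the score fails to capture is not adjusted for later in the primary analysis. Matching can balance only the recorded flag, and Tables 2 and 3 can report only the recorded flag. A small standardized difference could then reflect under-recording rather than comparable arms.

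Section 7 makes a severity difference between arms plausible. It says that soft mist inhalers "may help preserve benefits in patients with diminished peak inspiratory flow rates". If prescribers act on that reasoning, sicker patients would go more often to Stiolto.

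**Working it through.** **1. Text check.** The plan states no figure for oxygen use or its capture, so there is nothing to reproduce.

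- Definition: one word in Annex 3, with no code in Annex 4 or elsewhere.
- Matching field: none is stated for Annex 3. Where the plan does say how drugs are matched, it uses names: NDC generic and brand name for the exposures (section 9.3.1), and generic name within the dementia measure (Annex 4).
- Use: propensity score, multivariable models, Tables 2 and 3.
- Alternative route: Outpatient Services is available (section 9.4), and HCPCS codes are already used for other measures (Annex 4).

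**2. Illustration of size.** All inputs here are assumptions. Let p1 and p0 be the true prevalence of oxygen use in the Stiolto and Anoro arms, s the share of users that the definition captures (equal in both arms, with no false positives), and HR the hazard ratio of oxygen use for discontinuation.

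True prevalence among patients coded 'no': q = p(1 − s)/(1 − ps).

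Distortion of the treatment hazard ratio in that group: B = (1 + q1(HR − 1))/(1 + q0(HR − 1)).

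Example with p1 = 0.30, p0 = 0.20, HR = 2.0, s = 0.5: q1 = 0.15/0.85 = 0.176; q0 = 0.10/0.90 = 0.111; B = 1.176/1.111 = 1.059.

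| p1 v p0 | HR | s = 0 | s = 0.1 | s = 0.5 | s = 0.9 |
|---|---|---|---|---|---|
| 0.15 v 0.10 | 1.25 | 1.012 | 1.011 | 1.007 | 1.002 |
| 0.15 v 0.10 | 2.0 | 1.045 | 1.042 | 1.027 | 1.006 |
| 0.25 v 0.20 | 1.25 | 1.012 | 1.011 | 1.008 | 1.002 |
| 0.25 v 0.20 | 2.0 | 1.042 | 1.040 | 1.029 | 1.008 |
| 0.30 v 0.20 | 1.25 | 1.024 | 1.023 | 1.016 | 1.004 |
| 0.30 v 0.20 | 2.0 | 1.083 | 1.080 | 1.059 | 1.016 |

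Two further cases with s = 0:
- 0.20 v 0.15, HR 1.2: (1 + 0.20 × 0.2)/(1 + 0.15 × 0.2) = 1.04/1.03 = 1.010.
- 0.20 v 0.10, HR 1.6: (1 + 0.20 × 0.6)/(1 + 0.10 × 0.6) = 1.12/1.06 = 1.057.

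If p1 = p0, then q1 = q0 and B = 1. If oxygen users are more persistent, B falls below 1. For example, with HR = 0.8, 0.30 v 0.20 and s = 0, B = 0.94/0.96 = 0.979. The formula ignores correlation with other covariates in the score, which would bring B closer to 1.

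**3. Effect on the balance table before matching.** Take true prevalence of 0.30 v 0.20. The true standardized difference is 0.10/√((0.21 + 0.16)/2) = 0.10/0.430 = 0.23. With s = 0.1 the recorded prevalences are 0.03 and 0.02, and the recorded difference is 0.01/√((0.0291 + 0.0196)/2) = 0.01/0.156 = 0.06. Low capture alone makes the arms look closer than they are.

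**The case against.** The strongest reply is that the documents do not say how oxygen is billed or which field the word is matched against. Annex 3 also contains class labels, such as rapid-acting insulin and beta-blockers, which cannot be literal product names, so 'Oxygen' may be shorthand for a fuller list. This stands against any claim about how much is missed. A reader might infer that the flag will be nearly empty and that most oxygen users will be coded 'no'. That needs the billing route and the captured share, and the plan gives neither. It does not rescue the definition: names are the only drug-matching method that the plan states, and if another field is meant the measure cannot be reproduced from the text.

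Second, sections 9.8 and 9.12 provide for tabulating every variable, medical review of code lists and changes to definitions, and Table 2 would show a very low oxygen count by arm. These steps could reveal the problem, but they do not supply the missing codes, and partial capture would be hard to see.

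Third, a reader might treat oxygen as one of the few severity markers. The documents do not support this: section 9.3.3 also lists oral corticosteroids, the respiratory inhaler classes, oral antibiotics, respiratory hospitalization, emergency visits, exertional breathlessness and lung function tests. These would absorb part of any distortion. They do not fully replace oxygen: the test covariates record that a test was done, not its result, and the respiratory hospitalization measure requires an inpatient principal diagnosis.

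Fourth, channelling of sicker patients to Stiolto is plausible from section 7, but the plan reports no prescribing pattern and calls the role of the device an open question. It should not be described as expected. Section 9.9 already concedes residual confounding in general.

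**Conclusion.** The point holds in a limited form. The definition of oxygen therapy has no code, departs from how the plan handles other measures that depend on procedures or equipment, and would turn use recorded only under codes into 'no' for a covariate in the score and the models. The degree of under-capture cannot be judged from the documents.

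The likely effect on the hazard ratio is modest: about 1.00 to 1.08 over a prevalence difference of 5 to 10 points, a hazard ratio for oxygen use of 1.2 to 2.0, and capture from none to 90%. That range rests wholly on assumed inputs. It does not show that the primary result is materially biased. The reason to act is that better capture of a confounder the plan has already chosen is available at almost no cost.

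**What to change.** Define Oxygen Therapy in Annex 4 as at least 1 inpatient or outpatient claim in the 180-day baseline with an HCPCS code for oxygen equipment or contents, or a diagnosis code for dependence on supplemental oxygen, in addition to any pharmacy record. State which field the pharmacy name is matched against. Use this flag in the propensity score, the multivariable models and Tables 2 and 3, and check its prevalence by arm before matching.

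The cost is one more code list to build, to be reviewed with the others under section 9.12, and an amendment entry as section 9.8 requires. No new data are needed.

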## ANNEX 4. LIST OF COMORBIDITY, SYMPTOMS AND OTHER MEASURE DEFINITIONS

Name	Definition
Comorbidities/Symptoms	
History of All-Cause Hospitalization	All inpatient events
History of Emergency Department Visit	1 Outpatient 
 
• Place of Service is any of: 
 
○ Emergency Room - Hospital
 
○ Urgent Care Facility
 
 
 

History of Hospitalization due to Respiratory Condition	1 Inpatient 
Diagnosis Code (Principal), ICD-9 is any of: { "415.1", "415.11", "415.12", "415.13", "415.19", "465", "465.0", "465.8", "465.9", "466", "466.0", "466.1", "466.11", "466.19", "480.0", "480.1", "480.2", "480.3", "480.8", "480.9", "481", "482.0", "482.1", "482.2", "482.30", "482.31", "482.32", "482.39", "482.40", "482.41", "482.42", "483.0", "483.1", "483.8", "484.1", "484.3", "484.5", "484.6", "484.7", "484.8", "486", "487.0", "488.01", "488.11", "488.81", "490", "491", "491.0", "491.1", "491.2", "491.20", "491.21", "491.22", "491.8", "491.9", "492.0", "492.8", "493.0", "493.00", "493.01", "493.02", "493.1", "493.10", "493.11", "493.12", "496", "515", "516.3", "516.30", "516.31", "516.32", "516.8", "516.9", "518.81", "518.83", "518.84" }
 
Diagnosis Code (Principal), ICD-10 is any of: { "A01.03", "A02.22", "A37.01", "A37.11", "A37.81", "A37.91", "A40.3", "A50.04", "A54.84", "B01.2", "B05.2", "B06.81", "B77.81", "B95.3", "B96.0", "B96.1", "I26.9", "I26.90", "I26.92", "I26.99", "J06", "J06.0", "J06.9", "J09.X1", "J09.X2", "J10.0", "J10.00", "J10.01", "J10.08", "J10.1", "J11.0", "J11.00", "J11.08", "J11.1", "J12", "J12.0", "J12.1", "J12.2", "J12.3", "J12.8", "J12.81", "J12.89", "J12.9", "J13", "J14", "J15", "J15.0", "J15.1", "J15.2", "J15.20", "J15.21", "J15.211", "J15.212", "J15.29", "J15.3", "J15.4", "J15.5", "J15.6", "J15.7", "J15.8", "J15.9", "J16", "J16.0", "J16.8", "J17", "J18", "J18.0", "J18.1", "J18.2", "J18.8", "J18.9", "J20", "J20.0", "J20.1", "J20.2", "J20.3", "J20.4", "J20.5", "J20.6", "J20.7", "J20.8", "J20.9", "J21.0", "J22", "J39", "J39.3", "J39.8", "J39.9", "J40", "J41", "J41.0", "J41.1", "J41.8", "J42", "J43", "J43.0", "J43.1", "J43.2", "J43.8", "J43.9", "J44.0", "J45", "J45.2", "J45.20", "J45.21", "J45.22", "J45.3", "J45.30", "J45.31", "J45.32", "J45.4", "J45.40", "J45.41", "J45.42", "J45.5", "J45.50", "J45.51", "J45.52", "J45.9", "J45.90", "J45.901", "J45.902", "J45.909", "J45.99", "J45.991", "J45.998", "J47.0", "J68.0", "J84.111", "J84.116", "J84.117", "J84.2", }

	“J85.1”, “J96”, “J96.9”, “J96.90”, “J96.91”, “J96.92”, “J96.0”, “J96.00”, “J96.01”, “J96.02”, “J96.1”, “J96.10”, “J96.11”, “J96.12”, “J96.2”, “J96.20”, “J96.21”, “J96.22”, “J98”, “J98.2”, “J98.3”, “J98.8” }
Acute Myocardial Infarction	
1 Inpatient or 1 Outpatient
 
Diagnosis Code (Position 1), ICD-9 is any of: { “410”, “410.0”, “410.00”, “410.01”, “410.1”, “410.10”, “410.11”, “410.2”, “410.20”, “410.21”, “410.3”, “410.30”, “410.31”, “410.4”, “410.40”, “410.41”, “410.5”, “410.50”, “410.51”, “410.6”, “410.60”, “410.61”, “410.7”, “410.70”, “410.71”, “410.8”, “410.80”, “410.81”, “410.9”, “410.90”, “410.91” }
 
Diagnosis Code (Principal), ICD-10 is any of: { “I21.09”, “I21.11”, “I21.19”, “I21.29”, “I21.3”, “I21.4”, “I22.0”, “I22.1”, “I22.2”, “I22.8”, “I22.9” }

Angina Pectoris	
1 Inpatient or 2 Outpatient (30 – 365 days apart)
 
Diagnosis Code (Any Position), ICD-9 is any of: { “413”, “413.0”, “413.1”, “413.9” }
 
Diagnosis Code (Any Position), ICD-10 is any of: { “I20.1”, “I20.8”, “I20.9” }

Peripheral Vascular Disease	
1 Inpatient or 2 Outpatient (30 – 365 days apart)
 
Diagnosis Code (Any Position), ICD-9 is any of: { “440”, “440.0”, “440.1”, “440.2”, “440.20”, “440.21”, “440.22”, “440.23”, “440.24”, “440.29”, “440.3”, “440.30”, “440.31”, “440.32”, “440.4”, “440.8”, “440.9”, “441”, “441.0”, “441.00”, “441.01”, “441.02”, “441.03”, “441.1”, “441.2”, “441.3”, “441.4”, “441.5”, “441.6”, “441.7”, “441.9”, “442”, “442.0”, “442.1”, “442.2”, “442.3”, “442.8”, “442.81”, “442.82”, “442.83”, “442.84”, “442.89”, “442.9”, “443.1”, “443.2”, “443.21”, “443.22”, “443.23”, “443.24”, “443.29”, “443.8”, “443.81”, “443.82”, “443.89”, “443.9”, “447.1”, “785.4”, “38.13”, “38.14”, “38.16”, “38.18”, “38.33”, “38.34”, “38.36”, “38.38”, “38.43”, “38.44”, “38.46”, “38.48”, “39.22”, “39.23”, “39.24”, “39.25”, “39.26”, “39.29” }
 
Diagnosis Code (Any Position), ICD-10 is any of: { “I70.0”, “I70.1”, “I70.209”, “I70.219”, “I70.229”, “I70.25”, “I70.269”, “I70.299”, “I70.399”, “I70.499”, “I70.599”, “I70.8”, “I70.90”, “I70.91”, “I70.92”, “I71.00”, “I71.01”, “I71.02”, “I71.03”, “I71.1”, “I71.2”, “I71.3”, “I71.4”, “I71.5”, “I71.6”, “I71.8”, “I71.9”, “I72.0”, “I72.1”, “I72.2”, “I72.3”, “I72.4”, “I72.8”, “I72.9”, “I73.1”, “I73.81”, “I73.89”, “I73.9”, “I77.1”, “I77.71”, “I77.72”, “I77.73”, “I77.74”, “I77.79”, “I79.8”, “I96” }

Heart Failure	
1 Inpatient
 
Diagnosis Code (Any Position), ICD-9 is any of: { “428”, “428.0”, “428.1”, “428.2”, “428.20”, “428.21”, “428.22”, “428.23”, “428.3”, “428.30”, “428.31”, “428.32”, “428.33”, “428.4”, “428.40”, “428.41”, “428.42”, “428.43”, “428.9” }
 
Diagnosis Code (Any Position), ICD-10 is any of: { “I50”, “I50.9”, “I50.2”, “I50.20”, “I50.21”, “I50.22”, “I50.23”, “I50.3”, “I50.30”, “I50.31”, “I50.32”, “I50.33”, “I50.4”, “I50.40”, “I50.41”, “I50.42”, “I50.43” }

Hypertension	
1 Inpatient or 2 Outpatient (30 – 365 days apart)
 
Diagnosis Code (Any Position), ICD-9 is any of: { “401”, “401.0”, “401.1”, “401.9”, “402”, “402.0”, “402.00”, “402.1”, “402.10”, “402.9”, “402.90”, “403”, “403.0”, “403.00”, “403.01”, “403.1”, “403.10”, “403.11”, “403.9”, “403.90”, “403.91”, “404”, “404.0”, “404.00”, “404.01”, “404.02”, “404.03”, “404.1”, “404.10”, “404.11”, “404.12”, “404.13”, “404.9”, “404.90”, “404.91”, “404.92”, “404.93”, “405”, “405.0”, “405.01”, “405.09”, “405.1”, “405.11”, “405.19”, “405.9”, “405.91”, “405.99” }
 
Diagnosis Code (Any Position), ICD-10 is any of: { “I10”, “I11.9”, “I12.0”, “I12.9”, “I13.0”, “I13.10”, “I13.11”, “I13.2”, “I15.0”, “I15.8” }

Upper Respiratory Infection (with no sinusitis)	
1 Inpatient or 2 Outpatient (30 – 365 days apart)
 
Diagnosis Code (Any Position), ICD-9 is any of: { “034”, “034.0”, “034.1”, “460”, “461”, “461.0”, “461.1”, “461.2”, “461.3”, “461.8”, “461.9”, “462”, “463”, “464”, “464.0”, “464.00”, “464.01”, “464.1”, “464.10”, “464.11”, “464.2”, “464.20”, “464.21”, “464.3”, “464.30”, “464.31”, “464.4”, “464.5”, “464.50”, “464.51”, “465”, “465.0”, “465.8”, “465.9”, “487”, “487.1”, “487.8” }
 
Diagnosis Code (Any Position), ICD-10 is any of: { “J03.00”, “J03.01”, “A38”, “A38.8”, “A38.9”, “J00”, “J01”, “J01.9”, “J01.90”, “J01.8”, “J01.80”, “J01.0”, “J01.00”, “J01.01”, “J32.0”, “J01.1”, “J01.10”, “J01.11”, “J32.1”, “J01.2”, “J01.20”, “J01.21”, “J32.2”, “J01.3”, “J01.30”, “J01.31”, “J32.3”, “J02”, “J02.8”, “J02.9”, “J04”, “J04.0”, “J05”, “J05.0”, “J04.1”, “J04.10”, “J04.11”, “J04.2”, “J05.1”, “J05.10”, “J05.11”, “J04.3”, “J04.30”, “J04.31”, “J06”, “J06.9”, “J11.89”, “J11.8”, “J11.1”, “J11”, “J10.89”, “J10.8”, “J10.1”, “J10.00”, “J10.0”, “J10”, “J09.X2”, “J09.X9”, }

	“J09.X”, “J09” }
Lower Respiratory Infection	
1 Inpatient or 2 Outpatient (30 – 365 days apart)
 
Diagnosis Code (Any Position), ICD-9 is any of: { “466”, “466.0”, “466.1”, “466.11”, “466.19” }
 
Diagnosis Code (Any Position), ICD-10 is any of: { “J20.9”, “J21.0”, “J21.8”, “J22” }

Cardiac Arrhythmias	
1 Inpatient or 1 Outpatient
 
Diagnosis Code (Principal), ICD-9 is any of: { “427”, “427.0”, “427.1”, “427.2”, “427.3”, “427.31”, “427.32”, “427.4”, “427.41”, “427.42”, “427.5”, “427.6”, “427.60”, “427.61”, “427.69”, “427.8”, “427.81”, “427.89”, “427.9” }
 
Diagnosis Code (Position 1), ICD-10 is any of: { “I46.9”, “I47.1”, “I47.2”, “I47.9”, “I48.91”, “I48.92”, “I49.01”, “I49.02”, “I49.1”, “I49.3”, “I49.40”, “I49.49”, “I49.5”, “I49.8”, “I49.9”, “R00.1” }

Cerebrovascular Disease	
1 Inpatient
 
Diagnosis Code (Any Position), ICD-9 is any of: { “430”, “431”, “432”, “432.0”, “432.1”, “432.9”, “433”, “433.0”, “433.01”, “433.1”, “433.11”, “433.2”, “433.21”, “433.3”, “433.31”, “433.8”, “433.81”, “433.9”, “433.91”, “434”, “434.0”, “434.01”, “434.1”, “434.11”, “434.9”, “434.90”, “434.91”, “435”, “435.8”, “435.9”, “436” }
 
Diagnosis Code (Any Position), ICD-10 is any of: { “G45”, “G45.8”, “G45.9”, “I60”, “I60.0”, “I60.00”, “I60.01”, “I60.02”, “I60.1”, “I60.10”, “I60.11”, “I60.12”, “I60.2”, “I60.20”, “I60.21”, “I60.22”, “I60.3”, “I60.30”, “I60.31”, “I60.32”, “I60.4”, “I60.5”, “I60.50”, “I60.51”, “I60.52”, “I60.6”, “I60.7”, “I60.8”, “I60.9”, “I61”, “I61.0”, “I61.1”, “I61.2”, “I61.3”, “I61.4”, “I61.5”, “I61.6”, “I61.8”, “I61.9”, “I62”, “I62.0”, “I62.00”, “I62.01”, “I62.02”, “I62.03”, “I62.1”, “I62.9”, “I63”, “I63.0”, “I63.00”, “I63.01”, “I63.011”, “I63.012”, “I63.019”, “I63.02”, “I63.03”, “I63.031”, “I63.032”, “I63.039”, “I63.09”, “I63.1”, “I63.10”, “I63.11”, “I63.111”, “I63.112”, “I63.119”, “I63.12”, “I63.13”, “I63.131”, “I63.132”, “I63.139”, “I63.19”, “I63.2”, “I63.20”, “I63.21”, “I63.211”, “I63.212”, “I63.219”, “I63.22”, “I63.23”, “I63.231”, “I63.232”, “I63.239”, “I63.29”, “I63.3”, “I63.30”, “I63.31”, “I63.311”, “I63.312”, “I63.319”, “I63.32”, “I63.321”, “I63.322”, “I63.329”, “I63.33”, “I63.331”, “I63.332”, “I63.339”, “I63.34”, “I63.341”, “I63.342”, “I63.349”, “I63.39”, “I63.4”, “I63.40”, “I63.41”, “I63.411”, “I63.412”, “I63.419”, “I63.42”, “I63.421”, “I63.422”, “I63.423” }

	
“I63.429”, “I63.43”, “I63.431”, “I63.432”, “I63.439”, “I63.44”, “I63.441”, “I63.442”, “I63.449”, “I63.49”, “I63.5”, “I63.50”, “I63.51”, “I63.511”, “I63.512”, “I63.519”, “I63.52”, “I63.521”, “I63.522”, “I63.529”, “I63.53”, “I63.531”, “I63.532”, “I63.539”, “I63.54”, “I63.541”, “I63.542”, “I63.549”, “I63.59”, “I63.6”, “I63.8”, “I63.9”, “I65”, “I65.0”, “I65.01”, “I65.02”, “I65.03”, “I65.09”, “I65.1”, “I65.2”, “I65.21”, “I65.22”, “I65.23”, “I65.29”, “I65.8”, “I65.9”, “I66”, “I66.0”, “I66.01”, “I66.02”, “I66.03”, “I66.09”, “I66.1”, “I66.11”, “I66.12”, “I66.13”, “I66.19”, “I66.2”, “I66.21”, “I66.22”, “I66.23”, “I66.29”, “I66.3”, “I66.8”, “I66.9” }

All Cancers (except nonmelanoma skin cancer)	
1 Inpatient or 2 Outpatient (30 – 365 days apart)
 
Diagnosis Code (Any Position), ICD-9 is any of: { “140”, “140.0”, “140.1”, “140.3”, “140.4”, “140.5”, “140.6”, “140.8”, “140.9”, “141”, “141.0”, “141.1”, “141.2”, “141.3”, “141.4”, “141.5”, “141.6”, “141.8”, “141.9”, “142”, “142.0”, “142.1”, “142.2”, “142.8”, “142.9”, “143”, “143.0”, “143.1”, “143.8”, “143.9”, “144”, “144.0”, “144.1”, “144.8”, “144.9”, “145”, “145.0”, “145.1”, “145.2”, “145.3”, “145.4”, “145.5”, “145.6”, “145.8”, “145.9”, “146”, “146.0”, “146.1”, “146.2”, “146.3”, “146.4”, “146.5”, “146.6”, “146.7”, “146.8”, “146.9”, “147”, “147.0”, “147.1”, “147.2”, “147.3”, “147.8”, “147.9”, “148”, “148.0”, “148.1”, “148.2”, “148.3”, “148.8”, “148.9”, “149”, “149.0”, “149.1”, “149.8”, “149.9”, “150”, “150.0”, “150.1”, “150.2”, “150.3”, “150.4”, “150.5”, “150.8”, “150.9”, “151”, “151.0”, “151.1”, “151.2”, “151.3”, “151.4”, “151.5”, “151.6”, “151.8”, “151.9”, “152”, “152.0”, “152.1”, “152.2”, “152.3”, “152.8”, “152.9”, “153”, “153.0”, “153.1”, “153.2”, “153.3”, “153.4”, “153.5”, “153.6”, “153.7”, “153.8”, “153.9”, “154”, “154.0”, “154.1”, “154.2”, “154.3”, “154.8”, “155”, “155.0”, “155.1”, “155.2”, “156”, “156.0”, “156.1”, “156.2”, “156.8”, “156.9”, “157”, “157.0”, “157.1”, “157.2”, “157.3”, “157.4”, “157.8”, “157.9”, “158”, “158.0”, “158.8”, “158.9”, “159”, “159.0”, “159.1”, “159.8”, “159.9”, “160”, “160.0”, “160.1”, “160.2”, “160.3”, “160.4”, “160.5”, “160.8”, “160.9”, “161”, “161.0”, “161.1”, “161.2”, “161.3”, “161.8”, “161.9”, “162”, “162.0”, “162.2”, “162.3”, “162.4”, “162.5”, “162.8”, “162.9”, “163”, “163.0”, “163.1”, “163.8”, “163.9”, “164”, “164.0”, “164.1”, “164.2”, “164.3”, “164.8”, “164.9”, “165”, “165.0”, “165.8”, “165.9”, “170”, “170.0”, “170.1”, “170.2”, “170.3”, “170.4”, “170.5”, “170.6”, “170.7”, “170.8”, “170.9”, “171”, “171.0”, “171.2”, “171.3”, “171.4”, “171.5”, “171.6”, “171.7”, “171.8”, “171.9”, “174”, “174.0”, “174.1”, “174.2”, “174.3”, “174.4”, “174.5”, “174.6”, “174.8”, “174.9”, “175”, “175.0”, “175.9”, “176”, “176.0”, “176.1”, “176.2”, “176.3”, “176.4”, “176.5”, “176.8”, “176.9”, “179”, “180”, “180.0”, “180.1”, “180.8”, “180.9”, “181”, “182”, “182.0”, “182.1”, “182.8”, “183”, “183.0”, “183.2”, “183.3”, “183.4”, “183.5”, “183.8”, “183.9”, “184”, “184.0”, “184.1”, “184.2”, “184.3”, “184.4”, “184.8”, “184.9”, “185”, “186”, “186.0”, “186.9”, “187”, “187.1”, “187.2”, “187.3”, “187.4”, “187.5”, “187.6”, “187.7”, “187.8”, “187.9”, “188”, “188.0”, “188.1”, “188.2”, “188.3”, “188.4”, “188.5”, “188.6”, “188.7”, “188.8”, “188.9”, “189”,


Proprietary confidential information © 2019 Boehringer Ingelheim International GmbH or one or more of its affiliated companies.

“202.84”, “202.85”, “202.86”, “202.87”, “202.88”, “202.9”, “202.90”, “202.91”, “202.92”, “202.93”, “202.94”,  
 “202.95”, “202.96”, “202.97”, “202.98”, “203”, “203.0”, “203.00”, “203.01”, “203.02”, “203.1”, “203.10”, “203.11”,  
 “203.12”, “203.8”, “203.80”, “203.81”, “203.82”, “204”, “204.0”, “204.00”, “204.01”, “204.02”, “204.1”, “204.10”,  
 “204.11”, “204.12”, “204.2”, “204.20”, “204.21”, “204.22”, “204.8”, “204.80”, “204.81”, “204.82”, “204.9”,  
 “204.90”, “204.91”, “204.92”, “205”, “205.0”, “205.00”, “205.01”, “205.02”, “205.1”, “205.10”, “205.11”, “205.12”,  
 “205.2”, “205.20”, “205.21”, “205.22”, “205.3”, “205.30”, “205.31”, “205.32”, “205.8”, “205.80”, “205.81”,  
 “205.82”, “205.9”, “205.90”, “205.91”, “205.92”, “206”, “206.0”, “206.00”, “206.01”, “206.02”, “206.1”, “206.10”,  
 “206.11”, “206.12”, “206.2”, “206.20”, “206.21”, “206.22”, “206.8”, “206.80”, “206.81”, “206.82”, “206.9”,  
 “206.90”, “206.91”, “206.92”, “207”, “207.0”, “207.00”, “207.01”, “207.02”, “207.1”, “207.10”, “207.11”, “207.12”,  
 “207.2”, “207.20”, “207.21”, “207.22”, “207.8”, “207.80”, “207.81”, “207.82”, “208”, “208.0”, “208.00”, “208.01”,  
 “208.02”, “208.1”, “208.10”, “208.11”, “208.12”, “208.2”, “208.20”, “208.21”, “208.22”, “208.8”, “208.80”,  
 “208.81”, “208.82”, “208.9”, “208.90”, “208.91”, “208.92”, “V10.82” }

Proprietary confidential information © 2019 Boehringer Ingelheim International GmbH or one or more of its affiliated companies

	“C92.00”, “C92.01”, “C92.02”, “C92.10”, “C92.11”, “C92.12”, “C92.20”, “C92.21”, “C92.22”, “C92.30”, “C92.31”, “C92.32”, “C92.40”, “C92.41”, “C92.42”, “C92.50”, “C92.51”, “C92.52”, “C92.90”, “C92.91”, “C92.92”, “C92.Z0”, “C92.Z1”, “C92.Z2”, “C93.00”, “C93.01”, “C93.02”, “C93.10”, “C93.11”, “C93.12”, “C93.90”, “C93.91”, “C93.92”, “C93.Z0”, “C93.Z1”, “C93.Z2”, “C94.00”, “C94.01”, “C94.02”, “C94.20”, “C94.21”, “C94.22”, “C94.30”, “C94.31”, “C94.32”, “C94.80”, “C94.81”, “C94.82”, “C95.00”, “C95.01”, “C95.02”, “C95.10”, “C95.11”, “C95.12”, “C95.90”, “C95.91”, “C95.92”, “C96.0”, “C96.4”, “C96.9”, “C96.A”, “C96.Z”, “D03.0”, “D03.10”, “D03.11”, “D03.12”, “D03.20”, “D03.21”, “D03.22”, “D03.30”, “D03.39”, “D03.4”, “D03.51”, “D03.52”, “D03.59”, “D03.60”, “D03.61”, “D03.62”, “D03.70”, “D03.71”, “D03.72”, “D03.8”, “D03.9”, “D45”, “D03”, “D03.1”, “D03.2”, “D03.3”, “D03.5”, “D03.6”, “D03.7”, “C43”, “C43.1”, “C43.11”, “C43.12”, “C43.2”, “C43.21”, “C43.22”, “C43.3”, “C43.5”, “C43.51”, “C43.52”, “C43.6”, “C43.61”, “C43.62”, “C43.7”, “C43.71”, “C43.72”, “Z85.820” }
Allergic Rhinitis	
1 Inpatient or 2 Outpatient (30 – 365 days apart)
 
Diagnosis Code (Any Position), ICD-9 is any of: { “477”, “477.0”, “477.1”, “477.2”, “477.8”, “477.9” }
 
Diagnosis Code (Any Position), ICD-10 is any of: { “J30”, “J30.1”, “J30.2”, “J30.5”, “J30.8”, “J30.81”, “J30.89”, “J30.9” }

Chronic Sinusitis	
1 Inpatient or 2 Outpatient (30 – 365 days apart)
 
Diagnosis Code (Any Position), ICD-9 is any of: { “473”, “473.0”, “473.1”, “473.2”, “473.3”, “473.8”, “473.9” }
 
Diagnosis Code (Any Position), ICD-10 is any of: { “J32”, “J32.0”, “J32.1”, “J32.2”, “J32.3”, “J32.4”, “J32.8”, “J32.9” }

Bronchiectasis	
1 Inpatient or 2 Outpatient (30 – 365 days apart)
 
Diagnosis Code (Any Position), ICD-9 is any of: { “011.5”, “011.50”, “011.51”, “011.52”, “011.53”, “011.54”, “011.55”, “011.56”, “494”, “494.0”, “494.1”, “748.61” }
 
Diagnosis Code (Any Position), ICD-10 is any of: { “J47.1”, “J47.9”, “Q33.4”, “J47”, “J47.0” }

Pneumonia	
1 Inpatient or 2 Outpatient (30 – 365 days apart)
 
Diagnosis Code (Any Position), ICD-9 is any of: { “003.22”, “020.3”, “020.4”, “020.5”, “021.2”, “022.1”, “031.0”, “039.1”, “052.1”, “055.1”, “073.0”, “083.0”, “112.4”, “114.0”, “114.4”, “114.5”, “115.05”, “115.15”, “115.95”, “130.4”, “136.3”, “480.0”, “480.1”, “480.2”, “480.3”, “480.8”, “480.9”, “481”, “482”, “482.0”, “482.1”, “482.2”, “482.3”, “482.30”, “482.31”, “482.32”, “482.39”, “482.4”, “482.40”, “482.41”, “482.42”, “482.49”, “482.8”, “482.81”, “482.82”, “482.83”, “482.84”, “482.89”, “482.9”, “483”, “483.0”, “483.1”, “483.8”, “484”, “484.1”, “484.3”, “484.5”, “484.6”, “484.7”, “484.8”, “485”, “486”, “487”, “487.0”, “487.1”, “487.8”, “517.1” }
 
Diagnosis Code (Any Position), ICD-10 is any of: { “A01.03”, “A02.22”, “A20.2”, “A21.2”, “A22.1”, “A31.0”, “A37.01”, “A37.11”, “A37.91”, “A43.0”, “A49.2”, “B01.2”, “B05.2”, “B06.81”, “B25.0”, “B37.1”, “B38.0”, “B38.1”, “B38.2”, “B39.0”, “B39.1”, “B39.2”, “B44.0”, “B58.3”, “B59”, “B77.81”, “J09”, “J09.X”, “J09.X1”, “J09.X2”, “J09.X9”, “J10”, “J10.0”, “J10.00”, “J10.01”, “J10.08”, “J10.1”, “J10.8”, “J10.89”, “J11”, “J11.0”, “J11.00”, “J11.08”, “J11.8”, “J11.89”, “J12.0”, “J12.1”, “J12.2”, “J12.3”, “J12.81”, “J12.89”, “J12.9”, “J13”, “J14”, “J15.0”, “J15.1”, “J15.20”, “J15.211”, “J15.212”, “J15.29”, “J15.3”, “J15.4”, “J15.5”, “J15.6”, “J15.7”, “J15.8”, “J15.9”, “J16.0”, “J16.8”, “J17”, “J18.0”, “J18.1”, “J18.8”, “J18.9” }

Chronic Bronchitis	
1 Inpatient or 2 Outpatient (30 – 365 days apart)
 
Diagnosis Code (Any Position), ICD-9 is any of: { “491”, “491.0”, “491.1”, “491.2”, “491.20”, “491.21”, “491.22”, “491.8”, “491.9” }
 
Diagnosis Code (Any Position), ICD-10 is any of: { “J41”, “J41.0”, “J41.1”, “J41.8”, “J42” }

Exertional Breathlessness	
1 Inpatient or 2 Outpatient (30 – 365 days apart)
 
Diagnosis Code (Any Position), ICD-10 is any of: { “R06.0*” }
 
Diagnosis Code (Any Position), ICD-9 is any of: { “786.0” }

Anxiety	
1 Inpatient or 2 Outpatient (30 – 365 days apart)
 
Diagnosis Code (Any Position), ICD-9 is any of: { “293.84”, “300.0”, “300.00”, “300.02”, “300.09”, “309.21”, “309.24”, “309.28”, “313.0” }
 
Diagnosis Code (Any Position), ICD-10 is any of: { “F06.4”, “F41.1”, “F41.8”, “F41.9”, “F43.22”, “F43.23”, “F93.0”, “F93.8”, “F40”, “F40.8”, “F40.9”, “F41”, “F41.0”, “F41.3” }

Dementia	
1 Inpatient or 2 Outpatient (30 – 365 days apart)
 
Diagnosis Code (Any Position), ICD-9 is any of: { “290.0”, “290.1”, “290.10”, “290.11”, “290.12”, “290.13”, “290.2”, “290.20”, “290.21”, “290.3”, “290.4”, “290.40”, “290.41”, “290.42”, “290.43”, “291.2”, “292.82”, “294.0”, “294.1”, “294.10”, “294.11”, “294.8”, “331.0”, “331.1”, “331.11”, “331.19”, “331.2”, “331.7”, “331.8”, “331.81”, “331.82”, “331.83”, “331.89”, “331.9”, “797” }
 
Diagnosis Code (Any Position), ICD-10 is any of: { “F01.50”, “F01.51”, “F02.80”, “F02.81”, “F03.90”, “F04”, “F05”, “F06.0”, “F06.8”, “F10.27”, “F19.97”, “G30.9”, “G31.01”, “G31.09”, “G31.1”, “G31.83”, “G31.84”, “G31.89”, “G31.9”, “G93.7”, “G94”, “R41.81”, “F32”, “F32.8”, “F33”, “F33.8” }
 
Generic Name is any of: { “DONEPEZIL HCL”, “GALANTAMINE HBR”, “RIVASTIGMINE”, “MEMANTINE HCL” }

Depression	
1 Inpatient or 2 Outpatient (30 – 365 days apart)
 
Diagnosis Code (Any Position), ICD-9 is any of: { “296.2”, “296.20”, “296.21”, “296.22”, “296.23”, “296.24”, “296.25”, “296.26”, “296.3”, “296.30”, “296.31”, “296.32”, “296.33”, “296.34”, “296.35”, “296.36”, “298.0”, “300.4”, “309.0”, “309.1”, “309.28”, “311” }
 
Diagnosis Code (Any Position), ICD-10 is any of: { “F32.0”, “F32.1”, “F32.2”, “F32.3”, “F32.4”, “F32.5”, “F32.9”, “F33.0”, “F33.1”, “F33.2”, “F33.3”, “F33.41”, “F33.42”, “F33.9”, “F34.1”, “F43.21”, “F43.23” }

Osteoporosis	1 Inpatient or 2 Outpatient (30 – 365 days apart)

